7.3. Pregnancy

Male subjects who are not surgically sterile, and are sexually active with a female partner must agree to use an effective method of birth control from the first administration of the study drug until 30 days after the last study drug application. Female subjects who are WOCBP, and are sexually active with a male partner must agree to use an effective method of birth control from the first administration of the study drug until 30 days after the last study drug application. Protocol Section 4.2, Inclusion Criteria #6, provides definitions of sterility and methods of acceptable birth control.

Prior to study enrollment, subjects must be advised of the importance of avoiding pregnancy during study participation and the potential risk factors for an unintentional pregnancy. The subject must sign an informed consent form documenting this discussion.

WOCBP should be instructed to contact the investigator immediately if they suspect they might be pregnant (e.g., missed or late menstrual period) during the study and for 30 days after she has completed her last test article application. If a subject or investigator suspects that a subject may be pregnant at any time during the study, the test article must be withheld until the results of laboratory pregnancy testing are available. If pregnancy is confirmed, the subject must not receive or apply further test article.

If following initiation of study treatment, it is subsequently discovered that a subject was pregnant or may have been pregnant at the time of test article exposure, the investigator must immediately notify the Medical Monitor of this event and record the pregnancy on the appropriate pregnancy surveillance form. The form will be sent to the Sponsor or designee. The investigator must notify the IRB of any pregnancy associated with the study treatment and keep careful source documentation of the event, including abortion (accidental, therapeutic, or spontaneous) and birth of offspring. Offspring should be followed for a minimum of eight weeks and any congenital anomaly/birth defect in a child born to a subject or a male subject's sexual partner that was exposed to the study drug should be documented on the pregnancy surveillance form as appropriate.

During the study, all male subjects should be instructed to contact the PI immediately if they suspect that their sexual partner might be pregnant (e.g., female sexual partner has missed or late menstrual period).

7.4. Toxicity Management

A dose mitigation strategy will be employed whereby, with Medical Monitor approval, the dose may be reduced/modified according to the individual subject's tolerance. Typical modification may include short drug holiday periods off therapy, every other day dosing, etc. Such changes however shall not be made without the written approval of the Medical Monitor.

8. STATISTICAL CONSIDERATIONS

8.1. Sample Size

No formal sample size calculations were performed for this study given it is an initial proof of concept study.

8.2. Analysis Populations

8.2.1. Safety Population

The Safety population will include all randomized subjects who received and applied study drug.

8.2.2. Intent-to-Treat Population

The ITT population will include all randomized subjects who were dispensed the study drug.

8.2.3. Per-Protocol Population

The PP population will include a subset of the ITT population who completed the study without significant protocol deviations (as will be determined prior to unblinding the randomization).

8.3. Endpoints

8.3.1. Primary Safety Endpoints

- Incidence (severity and causality) of any local and systemic AEs.
- Number of subjects with presence (and severity) of each LSR and each time point.
- Changes from Screening/Baseline in physical examination findings at Visit 5/EOT.
- Changes from Screening/Baseline in vital signs at Visit 5/EOT.
- Changes from Screening in local CBC at Visit 5/EOT.

8.3.2. Exploratory Engraftment Endpoint

- For skin engraftment assay, absolute and percent change from Screening to follow-ups in Cas5/PanBac and for follicular engraftment assay, the proportion of subjects with “success” at EOT where “success” is defined as a Follicular Biore® with “yes” outcome based on recovery of live NB01.

8.3.3. Exploratory Efficacy Endpoints

- Absolute change from Screening at each follow-up visit in IGA score.
- Absolute and percent change from Screening at each follow-up visit in total, inflammatory, and non-inflammatory lesions.

- Absolute and percent change from Screening to follow-up in Acne QoL.

8.3.4. Exploratory Sebum Endpoint

- Absolute and percent change from Screening to follow-up in sebum production.

8.4. Statistical Methods

All statistical processing will be performed using SAS[®]. Summary tables (descriptive statistics and/or frequency tables) will be provided for screening and/or baseline variables, efficacy variables, and safety variables. Summaries will be provided for each treatment group. In general, continuous variables will be summarized by descriptive statistics including sample size, mean, SD, median, minimum, and maximum. Categorical variables will be summarized by frequency and percentage.

8.4.1. Dosing Compliance

Descriptive statistics will be used to summarize for each treatment group the duration of treatment (defined as last dose date – first dose date +1), the total number of applications (determined from the doses reported in the Subject Diary), and the percent of expected doses applied for the ITT and PP populations. Subjects who apply at least 80% of the expected total number of applications and have no other evidence of material dosing non-compliance will be considered to be compliant with study drug dosing.

8.4.2. Primary Safety Analyses

All safety analyses will be performed on the Safety population.

Extent of Exposure

Descriptive statistics will be used to summarize the extent of exposure in the Safety population. The total amount of study drug used by each subject will be calculated based on the number of days the study drug was applied (according to the subject's diary entries).

Physical Examinations

Findings from the physical exam will be recorded in medical history (from assessment at Visit 1/Screening) or as AEs (from assessment at Visit 5/EOT).

Vital Signs

Descriptive statistics of vital signs (temperature, blood pressure, and heart rate) will be provided by treatment group.

Clinical Laboratory Tests

Local CBC tests will be evaluated for any material changes during the study period. All laboratory data will be listed and reported in the units received by the laboratory. Shift tables by analyte and by out of range flag will be presented.

Local Skin Reactions

The frequency of the individual LSRs (PI: erythema, edema, erosion/ulceration, scaling/dryness, and scabbing/crusting; Subject: itching and pain) will be tabulated by severity and treatment group at each visit. The frequency of the individual LSRs recorded by subjects in weekly diaries (redness, swelling, erosion/ulceration, scaling/dryness, and scabbing/crusting, itching, and pain) will be tabulated by severity and treatment group for each study week.

Adverse Events

All AEs reported during the study will be listed, documenting course, severity, PI assessment of the relationship to the study drug, and outcome. Verbatim terms on the eCRFs will be linked to preferred terms (PTs) and system organ class (SOC) using the Medical Dictionary for Regulatory Activities (MedDRA) mapping system. The PTs and SOC will then be tabulated. All reported AEs will be summarized by the number of subjects reporting AEs, SOC, PT, severity, and relationship to study drug by treatment group.

Urine Pregnancy Tests

Results from UPTs will be provided in a listing.

8.4.3. Exploratory Engraftment Analyses

The engraftment analyses will be conducted on the ITT and PP populations.

Engraftment Assay

For endpoint of Engraftment Assay of Cas5/PanBac, the absolute and percent change from Screening at each follow-up visit, the comparison between NB01 and vehicle-control will be analyzed using ANCOVA model with the dependent variable being absolute or percent change values and the factor treatment and the Screening value as a covariate in the model, with and without LOCF imputation.

For endpoint of Follicular Biore®, the treatment groups will be compared with respect to the proportions of subjects with “success” at Week 12 using the CMH test with and without stratification on study center, where “success” is defined as a Follicular Biore® with “yes” outcome based on the recovery of live NB01.

8.4.4. Exploratory Efficacy Analyses

The efficacy analyses will be conducted on the ITT and PP populations.

Investigator’s Global Assessment

The observed and change from Screening scores at each follow-up visit will be tabulated. For endpoint of IGA, the treatment groups will be compared with respect to the proportions of subjects with (a) at least a one-point improvement and (b) at least a two-point improvement in IGA score relative to Screening at each follow-up visit using the CMH test with and without stratification on study center.

Acne Lesion Counts

For endpoint of Acne Lesion Counts, the absolute and percent change from Screening at each follow-up visit in total, inflammatory, and non-inflammatory lesions, the comparison between NB01 and vehicle-control will be analyzed using Analysis of Covariance (ANCOVA) model with the factor treatment and the Screening counts as a covariate in the model, with and without Last Observation Carried Forward (LOCF) imputation.

Acne Quality of Life

For endpoint of Acne-QoL, the absolute and percent change from Screening at each follow-up visit on four domains separately and total, the comparison between NB01 and vehicle-control will be analyzed using ANCOVA model with the factor treatment and the Screening score as a covariate in the model, with and without LOCF imputation.

8.5. Exploratory Sebum Analyses

Sebum Production

For endpoint of sebum production, the absolute and percent change from Screening at each follow-up visit, the comparison between NB01 and vehicle-control will be analyzed using ANCOVA model with the factor treatment and the Screening value as a covariate in the model, with and without LOCF imputation.

8.6. Interim Analyses

No interim analyses are planned for this study.

9. RESPONSIBILITIES

9.1. Investigator Responsibilities

9.1.1. Good Clinical Practice

This study will be conducted in compliance with the principles of the Declaration of Helsinki, with the current Good Clinical Practice guidelines and with other applicable regulations. The PI and all study staff will conduct the study in compliance with this protocol. The protocol, informed consent documents, recruitment advertisements, and any amendments to these items will have IRB approval prior to study initiation. Voluntary informed consent will be given by every subject prior to the initiation of any study-related procedures. The rights, safety and well-being of the study subjects are the most important considerations and prevail over the interests of science and society. All personnel involved in the conduct of this study must be qualified by education, training, and experience to perform their assigned responsibilities. Contact information for each site and any clinical laboratories used in the study will be maintained up to date in a separate reference document.

9.1.2. Institutional Review Board Review and Approval

Before study initiation, the PI must have written and dated approval from the IRB for the protocol, consent form, subject recruitment materials/process (e.g., advertisements), and any other written information to be provided to the subject. The PI should also provide the IRB with a copy of the product labeling, information to be provided to the subject and any updates. The PI will submit documentation of the IRB approval to the Sponsor.

The IRB approved consent form must include all elements required by FDA, state, and local regulations, and may include appropriate additional elements.

9.1.3. Informed Consent

The PI/designee will explain the study to each potential subject and the subject must indicate voluntary consent by signing and dating the approved informed consent form. The PI must provide the subject with a copy of the consent form, in a language the subject understands.

The PI will maintain documentation that informed consent was obtained prior to the initiation of any study-specific procedures.

9.1.4. Confidentiality

All laboratory specimens, evaluation forms, reports, and other records will be identified in a manner designed to maintain subject confidentiality. All records will be kept in a secure storage area with limited access.

The study Sponsor, and its representatives, may review optional photographs taken during the study, but will not have access to other personal identifying information during review of these photographs. In order to protect subject privacy, a rectangular bar will be placed over subjects' eyes in the photographs, to help de-identify any photo(s) to be used in any of the publication or presentation materials described in [Section 9.2.3](#). Additionally, any features that could be used to identify subjects, such as a scars or tattoos, will also be covered in the photographs. Clinical information will not otherwise be released (with the exception of de-identified data described in [Section 9.2.3](#)) without the written permission of the subject, except as necessary for monitoring by TI or the Sponsor, the FDA or other regulatory authority, or the IRB.

The PI and all employees and coworkers involved with this study shall not disclose or use for any purpose other than performance of the study, any data, records, or other unpublished, confidential information disclosed to those individuals for the purpose of the study. Prior written agreement from TI or the Sponsor must be obtained for the disclosure of any said confidential information to other parties.

9.1.5. Study Files and Retention of Records

The PI must maintain all study records (including study drug disposition, informed consents, CRFs, source documents, correspondence, regulatory documents, contracts, etc.) for the maximum period required by the Sponsor or the institution where the study is conducted, whichever is longer. Study drug Accountability Logs and original Label Pages (if applicable) must be kept with study records at the site.

The PI must contact the Sponsor prior to destroying any records associated with this study.

If the PI withdraws from the study, the records shall be transferred to a mutually agreed upon designee. Written notification of such a transfer must be given to the Sponsor.

9.1.6. Case Report Forms

This study utilizes eCRFs; validated 21 CFR Part 11 compliant electronic data capture (EDC) software will be used to collect data. All requested information must be entered on the eCRFs in the areas provided in a timely manner. When changes or corrections are made in the eCRF, the EDC system will maintain a complete audit trail of the person making the changes, the date and time of the change, and the reason for the change. Only individuals who have completed EDC training and are listed on the Delegation of Responsibilities Log with responsibility for eCRF completion will be provided usernames and passwords in order to access the system and make entries on the eCRF.

The PI or physician sub-investigator must electronically sign and date each subject's eCRF. Individuals who will be providing electronic signatures must first submit documentation with a handwritten signature acknowledging that their electronic signature is a legally binding equivalent to their handwritten signature.

9.1.7. Inspections

Representatives from TI and/or the Sponsor or a third party selected by the Sponsor may conduct a quality assurance audit of this study. During the audit, the PI must provide the auditor with direct access to all relevant documents and discuss any findings with the auditor.

In the event of an inspection by the FDA or other regulatory authorities, the PI must give the inspector direct access to relevant documents and to discuss any findings with the inspector. The PI must notify TI in the event of an FDA site audit.

9.1.8. Protocol Compliance

The IRB approved protocol must be followed except in the case of a change that is intended to eliminate an immediate risk to subjects. All protocol deviations must be documented.

9.2. Sponsor Responsibilities

9.2.1. Protocol Modifications

The Sponsor will prepare all protocol revisions. All protocol amendments must receive IRB approval prior to implementation. All administrative letters must be submitted to the IRB for their information. Copies of all correspondence with the IRB regarding this study must be sent to TI.

New or altered consent forms required by the IRB due to a protocol change must be signed by all subjects currently enrolled in the study and must be used for any subsequent subject enrollment.

9.2.2. Access to Information for Monitoring, Auditing or Inspections

Representatives of the Sponsor and the Sponsor's CRO must be allowed to visit all study sites, to review study records, and to directly compare them with source documents (including, but not limited to patient and hospital records), to discuss the study conduct with the PI and study staff, and to verify that the PI, study staff, and facilities remain acceptable for the conduct of the study.

Representatives of government regulatory authorities may also evaluate the study records, source documents, PI, study staff, and facilities.

The PI should immediately notify the Sponsor of any audits of this study by any regulatory agency and must promptly provide copies of any audit reports.

9.2.3. Study Report and Publications

A clinical study report will be prepared and provided to the regulatory agency. Naked Biome will ensure that the report meets the standards set out in the ICH Guideline for Structure and Content

of Clinical Study Reports (ICH E3). NOTE: An abbreviated report may be prepared in certain cases.

The trial Sponsor may use de-identified data (including de-identified photographs) obtained during the study in scientific journals or magazines and as part of other presentations for corporate, research, medical, scientific, or educational purposes.

PIs in this study may communicate, orally present, or publish in scientific journals or other scholarly media only after the following conditions have been met:

1. The results of the study in their entirety have been publicly disclosed by or with the consent of Naked Biome in an abstract, manuscript, or presentation form or the study has been completed at the study site for at least two years.
2. The PI will submit to Naked Biome any proposed publication or presentation along with the respective scientific journal or presentation forum at least 30 days before submission of the publication or presentation.
3. No such communication, presentation, or publication will include Naked Biome's confidential information.
4. The PI will comply with Naked Biome's request to delete references to its confidential information (other than the study results) in any paper or presentation and agrees to withhold publication or presentation for an additional 60 days to obtain patent protection if deemed necessary.

10. END OF STUDY CRITERIA

At the end of each subject's participation in the study, the PI will complete an End of Study form for all completed and discontinued subjects.

10.1. Completion of the Study

Each subject who completes all study visits, as specified in this protocol will have completed the study.

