8. STATISTICAL METHODS

8.1 General Considerations

All statistical processing will be performed using SAS[®] version 9.4. Summary tables (descriptive statistics and/or frequency tables) will be provided for screening and/or baseline variables, efficacy variables, and safety variables. Summaries will be provided for each treatment group. In general, continuous variables will be summarized by descriptive statistics including sample size, mean, SD, median, minimum, and maximum. Categorical variables will be summarized by frequency and percentage.

In general, all tables will be supported by relevant listing (by-subject). Figures may be created to aid in the interpretation of results.

The by visit data analyses will be summarized and analyzed using the visit window for modified intent-to-treat (mITT) and per-protocol (PP) populations based on target day as shown in Table 3.

Table 3: Analyses Windows for mITT and PP Populations

Visit	Target Day	mITT Window	PP Window
Visit 1 / Screening	-28 to -1	-28 to -1	-28 to -1
Visit 2 / Baseline	1	1	1
Visit 3 / Week 2	8	2 – 21	6 – 10
Visit 4 / Week 7	43	22 – 61	36 – 50
Visit 5 / Week 12 / EOT	80	> 61	71– 90

If there is more than one measurement within a visit after windowing is applied, the one closest to the target day will be used in the analysis by visit. If a study visit is outside of the window in PP analyses, it will be treated as missing data.

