8.2 Analysis Populations

8.2.1 *Safety Population*

The Safety population will include all randomized subjects who received and applied study drug. Subjects will have their first application of test article applied in the clinic by the PI (or sub-I-designee) during their Baseline Visit on Day 1. Subjects will be included in a treatment group based on the treatment they received (even if not the treatment group to which they were randomized). If a subject administered more than one type of test article during the trial, then the subject will be included in the treatment group to which they were randomized.

8.2.2 *Modified Intent-to-Treat Population*

The modified intent-to-treat (mITT) population will include all randomized subjects who were dispensed the study drug and have at least one post-baseline assessment. Subjects will be included in the treatment group to which they were randomized, regardless of the treatment received.

8.2.3 *Per-Protocol Population*

The per-protocol (PP) population will include a subset of the mITT population who completed the study without significant protocol deviations (as will be determined prior to unblinding the randomization) and met the criteria as specified below. Subjects will be included in the treatment group based on the treatment received.

- Meets all inclusion criteria and does not meet exclusion criteria #1-11 and #13-22.
- Has not taken or applied any interfering concomitant medications/therapies.
- Completed Visit 5/EOT procedures on Days 71 to 90 with the visit occurring 1 to 10 days after the final application of test article.
- Applied at least 80% of the expected doses with no other evidence of material dosing non-compliance.

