8.3 Final Analyses and Reporting

An initial data freeze will occur once all subjects have completed the treatment period and all subject data through Visit 5/EOT has been monitored. Analysis populations will be identified and the Project Statistician will be unblinded in order to produce key summary tables that will be provided to the Sponsor. Final database lock will occur after all subjects have completed the study assessment period (or discontinued early) and all subject data has been monitored. The EOS visit captures safety (AE and LSR) data only.

Further exploratory analyses not necessarily identified in this SAP may be performed to support the clinical development program. Any post-hoc or unplanned analyses performed and not described in this SAP will be clearly identified in the CSR.

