8.11.4 Statistical / Analytical Issues

8.11.4.1 Handling of Dropouts or Missing Data

The primary method of handling missing data will be the MMRM method without explicit imputations for missing data. Since IGA is analyzed based on a “success” criteria (one- or two-point improvement in score), subjects with a missing IGA score will be considered a “failure” in the analysis for the mITT population. Analyses in the PP population will use observed data only.

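### The per-protocol set requires every study visit, including the safety-only Week 16 call, and this conflicts with fixing the set on data through Visit 5

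*Protocol*

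**What the plan says.** Protocol 8.2.3 defines the set this way: "The PP population will include a subset of the ITT population who completed the study without significant protocol deviations". SAP 8.2.3 keeps the phrase, starts from the mITT set, and joins a list of criteria to it with *and*: "completed the study without significant protocol deviations (as will be determined prior to unblinding the randomization) and met the criteria as specified below". One listed criterion concerns a visit: "Completed Visit 5/EOT procedures on Days 71 to 90 with the visit occurring 1 to 10 days after the final application of test article". Another requires at least 80% of expected doses.

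Neither PP definition says what completing the study means. Protocol 10.1 does: "Each subject who completes all study visits, as specified in this protocol will have completed the study". The scheduled visits run through Visit 6 at Week 16, which Protocol 3.6 and 6.2.4 describe as a telephone follow-up. SAP 8.3 says of it: "The EOS visit captures safety (AE and LSR) data only".

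Three other SAP rules bear on the point:

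- SAP 8.1, on timing: "If a study visit is outside of the window in PP analyses, it will be treated as missing data".
- SAP 8.11.4.1, on missing data: "Analyses in the PP population will use observed data only".
- SAP 8.3, on sequence: once treatment is over for all subjects and data through Visit 5/EOT have been monitored, the populations are identified and the project statistician is unblinded. Database lock follows after the full assessment period.

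**The concern.** PP membership is meant to pick out subjects whose treatment and outcome data follow the protocol closely enough to show what the product does when used as intended. The engraftment and efficacy comparisons made in that set end at Visit 5. A telephone call about four weeks later adds nothing to them. If the call is a condition of entry, membership depends on something that happens after the last outcome has been measured, and usable Visit 5 data are discarded in a trial of 36 subjects.

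The timing adds a practical problem. PP exclusions are to be settled before unblinding, but the statistician may be unblinded before all Week 16 calls are due. For the last-enrolled subjects the team would have to ignore the completion rule or decide PP status after unblinding. Two statisticians working from the same text could derive different PP sets.

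**Working it through.** The plan gives no attendance rate, dropout rate or power figure, so there is no figure of its own to reproduce. The check has four steps.

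**1. The definition chain.** PP requires completion (Protocol 8.2.3, SAP 8.2.3). Completion is defined only in Protocol 10.1, as all study visits. Visit 6 is a study visit (Protocol 6.2.4 and Appendix 2). In the SAP the Visit 5 criterion is additional to completion, because the two are joined by *and*; it does not define completion.

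**2. The sequence.** Appendix 2 puts Visit 5 at Day 80 and Visit 6 at Day 106 ± 3.

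- Nominal gap: 106 − 80 = 26 days.
- Range, using the PP window for Visit 5 (Days 71 to 90) and Days 103 to 109 for Visit 6: 103 − 90 = 13 days to 109 − 71 = 38 days.

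The freeze in SAP 8.3 waits only for Visit 5 data. If it falls within this gap after the last subject's Visit 5, Visit 6 completion is unknown for the latest subjects when the blind is broken.

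**3. Size of the effect of the call.** Let q be the assumed proportion who miss the Week 16 call, equal in both arms. Expected loss is 36 × q. The standard error is proportional to 1/√n, so its ratio is 1/√(1 − q).

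| q (assumed) | Subjects lost of 36 | SE ratio |
|---|---|---|
| 2% | 36 × 0.02 = 0.7 | 1/√0.98 = 1.01 |
| 5% | 36 × 0.05 = 1.8 | 1/√0.95 = 1.03 |
| 10% | 36 × 0.10 = 3.6 | 1/√0.90 = 1.05 |

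The counts are upper limits for each q, because some of the 36 would fail PP for other reasons.

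**4. Whether Visits 3 and 4 add to this.** Drug is handed out at Visits 2, 3 and 4 only (Appendix 2), in amounts meant to last until the next visit (Protocol 5.2.3). The unscheduled-visit list in Protocol 6.2.5 includes no dispensing. SAP 8.8 uses 75 doses as the denominator, so the 80% criterion needs 0.80 × 75 = 60 doses. Assume that supply lasts to the end of the next visit's window and that dosing is daily through Day 77.

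- Visit 3 missed: 10 doses (Days 1 to 10), then nothing until Visit 4, at the earliest Day 36 within its window. Days 36 to 77 give 42 more. Total 10 + 42 = 52, and 52/75 = 69%.
- Visit 4 missed: supply ends by Day 50, so at most 50 doses, and 50/75 = 67%.

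Both fall below 60. Such a subject would generally fail PP on dosing whatever completion means.

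**The case against.** The best case for leaving the text alone is that nobody would apply it literally. Protocol 10.1 says that attending all visits is enough for completion; it does not say that one missed visit makes a non-completer. The withdrawal reasons in Protocol 10.2 do not include a single missed visit. The only visit named in the SAP's PP criteria is Visit 5. Out-of-window PP visits become missing values and the subject is not removed on that ground. The sequence in SAP 8.3 makes no sense if Visit 6 counts.

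Much of this stands as evidence of intent, and neither document states the exclusion outright. It does not settle the matter. There is no other test of completion in either document. If completion meant Visit 5 only, the phrase would largely duplicate the Visit 5 criterion. SAP 8.3 itself separates the end of the treatment period from the end of the study assessment period, and the PP definition does not use the treatment-period wording. A programmer could reasonably take the completion status on the End of Study form (Protocol 10) as the PP flag.

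A reader might also infer that a missed Visit 3 or 4 costs PP many otherwise valid subjects. Requiring all three of Visits 3, 4 and 6, with 95% (90%) independent attendance at each, gives a loss of 1 − 0.95³ = 14% (1 − 0.90³ = 27%), about 5 (10) of 36. The documents do not support that size. Because of the supply schedule, wholly missing Visit 3 or 4 would generally breach the 80% dosing criterion already, unless extra drug was supplied outside the documented schedule. A visit held late does resupply drug, and SAP 8.1 covers it by setting the value to missing.

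**Conclusion.** The point holds for the Week 16 call. As written, PP entry depends on a safety-only contact after the last PP outcome, and the rule does not fit the SAP's own order of freeze, population assignment and unblinding. The timing conflict depends on the freeze coming before the last Visit 6, which SAP 8.3 allows but does not date.

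The effect is small: about 2 (4) of 36 subjects and about 3% (5%) on standard errors if 5% (10%) miss the call. Those rates are assumptions. Visits 3 and 4 add little, for the dosing reason shown above.

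The reach is limited. PP is used for the exploratory engraftment and efficacy analyses (SAP 8.9 and 8.11) and some descriptive summaries. The parallel mITT analyses do not change, and the primary safety analyses use the Safety population (SAP 8.12). A reader might count sebum among the affected analyses, but SAP 8.10 names no population for it. The change is still worth making, because it removes a stated rule that conflicts with the rest of the plan.

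**What to change.** In the PP definition (SAP 8.2.3 and Protocol 8.2.3), replace *completed the study* with *completed Visit 5/EOT*. Keep the Visit 5 window, the 80% dosing criterion and the other listed criteria.

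Add one sentence to SAP 8.2.3: a missed Visit 6 does not exclude a subject from PP, and a missing Visit 3 or 4 value is treated as missing data, in line with SAP 8.1. The sentence is needed because SAP 8.1 speaks of visits outside their window and does not expressly cover visits missed altogether.

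Keep the Protocol 10.1 definition for the disposition table in SAP 8.6. Make the change before populations are identified at the initial freeze. The cost is one phrase and one sentence, with no extra data or resources.
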